- ABLE/teleABLE: Activating Behavior for Lasting Engagement (name of intervention under study)
- ACS3: Activity Card Sort
- BIPOC: Black, Indigenous, People of Color
- CITI: Collaborative Institutional Training Initiative
- CKRI: Courage Kenny Rehabilitation Institute
- CTSI: Clinical and Translational Science Institute
- DoD: Department of Defense
- DWELL: Disability and WELLness Laboratory
- HIPAA: Health Information Portability and Accountability Act
- ICAN: Identify Choose Add/Adapt Notice
- ID: Identification
- IRB: Institutional Review Board
- ISP: Information Security and Privacy
- LGBTQ: Lesbian Gay Bisexual Transgender Queer
- M: Mean
- MoCA: Montreal Cognitive Assessment
- NIH: National Institutes of Health
- PI: Principal Investigator
- REDCap: Research Electronic Data Capture
- SD: Standard Deviation

Page 4 of 44

Template Revised On: 10/28/2022

NCT05029284

VERSION DATE: 07.21.2023

1.0 Objectives

1.1 Purpose: This project is a first step in trial planning for a future pilot randomized controlled trial which examines a remotely delivered intervention designed to reduce post-stroke sedentary behavior. The purpose of this project is to adapt the Activating Behavior for Lasting Engagement (ABLE) intervention protocol for remote delivery using videoconferencing, and to optimize trial study procedures in preparation for a future pilot randomized controlled trial. Our two goals in the present project are: 1) iteratively adapt the ABLE intervention to enable safe remote intervention delivery using videoconferencing (teleABLE), and 2) optimize acceptability of the teleABLE intervention and assessment procedures.

The PI has made draft adaptations to the ABLE intervention protocol in preparation for adapting ABLE to teleABLE. We will recruit 10 ambulatory, community-dwelling people with stroke who sustained their first-ever stroke ≤12 months prior to study enrollment and have access to a personal device that is compatible with videoconferencing (e.g. tablet, smartphone, computer). A sequential descriptive case series will be used to iteratively update the intervention protocol based on feedback from participants and therapists. Participants will complete assessments at 2 timepoints (baseline, 2-months), participate in 12 intervention sessions over 6 weeks, and complete 2 interviews. Findings from this study will result in a refined intervention and assessment protocol that will be deployed in a future randomized controlled trial examining the feasibility and effects of the teleABLE intervention.

Aim 1: Adapt the ABLE intervention protocol to enable safe remote intervention delivery using videoconferencing.

Hypothesis 1a: People with stroke and therapists will identify training content and intervention delivery strategies that support engagement in the teleABLE intervention (intervention interview, therapist documentation).

Hypothesis 1b: People with stroke and therapists will identify strategies that support safety during remotely delivered post-stroke intervention (intervention interview, study exist interview).

Aim 2: Optimize proposed trial study procedures (teleABLE intervention, assessment procedures) to enhance acceptability of trial design.

Hypothesis 2a: People with stroke will indicate satisfaction with teleABLE procedures (Client Satisfaction Questionnaire-8 mean item score ≥3).

Hypothesis 2b: People with stroke will recommend adaptations to intervention delivery and assessment sessions that optimize the study protocol (study exit interview).

2.0 Background

- 2.1 Significance of Research Question/Purpose: Sedentary lifestyles are prevalent among the 7 million Americans who have survived stroke, placing them at elevated risk for poor health outcomes [1, 2]. Approximately 81% of stroke survivors have at least one comorbid chronic condition, which elevated their risk for primary stroke and contributes to their ongoing risk for recurrent stroke [3]. These conditions heart disease, hypertension, diabetes, depression, and chronic obstructive pulmonary disorder persist and their management is compromised by sedentary behavior [4-8]. Reducing sedentary behavior is particularly important for promoting health in the context of stroke-related disability [9]. Even if impairments fully resolve, stroke survivors do not automatically re-engage in non-sedentary activities as impairments diminish [10]. Further, residual impairments, social influences (protective support persons), and environmental factors (transportation, accessibility) create barriers to engagement in personally meaningful non-sedentary daily activities [11-15].
- 2.2 Preliminary Data: The PI led the development and feasibility testing of the ABLE intervention targeting post-stroke sedentary behavior [16, 17]. Feasibility testing in 20 people with chronic stroke demonstrated that ABLE delivered in-person was safe, well tolerated, and able to be delivered by multiple therapists with high fidelity to the treatment protocol [17]. These promising results form the basis for the present research.
- Existing Literature: Interventions targeting post-stroke sedentary behavior are scant. Interventions that promoted adults' adherence to physical activity were less effective for reducing sedentary behavior than those specifically designed to reduce sedentary behavior [18]. Our systematic review of interventions that measured sedentary behavior or daily physical activity engagement as an outcome revealed only two interventions that specifically aimed to modify poststroke sedentary behavior [19]. The first (unnamed) employed motivational interviewing and action planning [20], while the second (STUFFS) used action planning in combination with feedback via an activity monitoring device [21]. To our knowledge, ABLE is the third intervention that specifically aims to reduce post-stroke sedentary behavior. The first two interventions facilitated physical activities (standing, walking, stepping, sit-to-stand exercise) during times when participants were at risk for sitting. A pilot randomized controlled trial of the motivational interviewing intervention demonstrated no between-group differences in sedentary behavior change relative to an attention control group which received diet advice. This intervention used a low dose (4 sessions delivered over 7 weeks) to achieve a 39.2 minutes per day within-group reduction in prolonged sitting [20]. It is likely that stroke survivors, who are adjusting to disability, require more structure, repetition, and intensity to achieve goals than adults without newly acquired disability. A single group feasibility study examined the STUFFS intervention during subacute stroke and demonstrated within-group reduction in sedentary time of 54.2 minutes per day, which diminished to 26.8

VERSION DATE: 07.21.2023

minutes per day at 8-week follow-up [21]. These findings are similar to results from the preliminary ABLE study.

The proposed adaptations to ABLE will build on existing literature. First, ABLE will be delivered earlier in the rehabilitation process than previously delivered. Sedentary lifestyles are established during the first year after stroke and persist through the chronic phase of stroke [22-24]. Delivering ABLE during this first year will capitalize on a period during which stroke survivors adopt new routines and seek strategies to reduce recurrent stroke risk [25, 26]. Second, ABLE will be delivered via telehealth (videoconference). Because participants complete scheduled activities between sessions, intervention sessions are primarily conversation-based. Thus, ABLE is readily adaptable to telehealth delivery (teleABLE), which will expand reach and access. Further, the COVID-19 pandemic accelerated support for implementation of telerehabilitation models [27, 28]. Simultaneously, this highlighted the need for evidence of safe and effective telerehabilitation interventions in stroke [29-33].

3.0 Study Endpoints/Events/Outcomes

- 3.1 Primary Endpoint/Event/Outcome: The primary outcome of this research is participant satisfaction as measured by:
 - Client Satisfaction Questionnaire-8 at week 8.
- 3.2 Secondary Endpoint(s)/Event(s)/Outcome(s): The secondary outcomes of this research focus on feasibility metrics and within-person change in behavioral outcomes.
 - Safety measured by documentation of treatment-related serious (e.g. injurious) and non-serious (e.g. fall without injury) adverse events that occur during the intervention period (weeks 2 through 7).
 - Enacted behavioral treatment dose measured by documentation of intervention session attendance (weeks 2 through 7).
 - Participation restrictions measured using the Activity Card Sort 3 (week 8).
 - Health-related quality of life measured using the EuroQoL-5 Dimension-5 Level (week 8).
 - Sedentary minutes measured using the activPAL micro3 monitor following an 8-day wear protocol (week 8).

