The intervention process is described in Table 2. Sessions 1 and 2 are focused on providing education regarding sedentary behavior, building awareness of personal sedentary behavior patterns, and identifying non-sedentary activities that are personally meaningful. The remaining sessions include an iterative process during which stroke survivors iteratively apply a 4-step strategy (ICAN Plan) that activates engagement in these non-sedentary daily activities. Participants Identify a time when they are at risk for sitting, **C**hoose an instrumental or daily activity to complete during that time, and create a specific plan to Adapt the activity by identifying solutions to anticipated barriers, and safety concerns. Participants are instructed to carry out the plan between sessions and Notice aspects of the plan that worked well or that may require a modified plan. Participants also notice how they felt during and after completing the activity. Within the Adapt step, participants are directly prompted to consider the safety of the activity and to develop a plan to assure safety. Therapists will follow the teleABLE Safety Algorithm (included with submission) to support participant dignity and safety. The ICAN process is documented on worksheets provided in the teleABLE workbook. This process guides participants through monitoring, scheduling, problem solving, and self-assessing activity engagement. This strategy enables teleABLE to be individualized to overcome participants' specific impairment and environmental barriers to engagement in preferred nonsedentary activities.

NCT05029284

VERSION DATE: 07.21.2023

Table 2. teleABLE intervention process

Week	Session	Content	Homework
1	1	Overview:What is sedentary behavior?Modifying sedentary behavior patterns	Self-monitor 1 day
	2	 Reflection: activPAL data, self-monitoring Brainstorm non-sedentary activities Introduce ICAN Plan 	Carry out ICAN PlanSelf-monitor 1 day
2 to 6 3 to 12		 Iterative process: Self-Assessment of ICAN Plan, Modify existing ICAN Plan, or Develop new ICAN Plan 	Carry out ICAN PlanSelf-monitor 1 day

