4.2 Drug/Device Handling: N/A

4.3 Biosafety: N/A

4.4 Stem Cells: N/A

4.5 Fetal Tissue: N/A

5.0 Procedures Involved

- 5.1 Study Design: This study uses a sequential case series design to refine the intervention and study protocol based on feedback from participants and the treating therapists. Participants will complete assessments at Baseline (week 1) and 2-months (week 8), participate in 12 intervention sessions over 6 weeks (weeks 2 through 7), and complete 2 interviews (mid-intervention and week 8). Participants will also wear an activPAL activity monitor for 8 days at baseline and 2-months to assess sedentary behavior.
- 5.2 Study Procedures: Participants will be recruited through Courage Kenny Rehabilitation Institute, community-based recruitment, and Fairview Health System (see section 11.1 to 11.3). Interested potential participants will complete a screening questionnaire over the telephone (see section 8.3). Those deemed eligible will meet with study staff to review the informed consent document and have an opportunity to ask questions before deciding whether they want to consent to participate in the study. Participants who choose to provide consent

Page 9 of 44

Template Revised On: 10/28/2022

VERSION DATE: 07.21.2023

will complete eConsent (see section 21.1). After providing consent, the participant will be scheduled to complete the baseline testing session. The schedule of measures is depicted in Table 3. All study procedures, including assessments and intervention sessions, will be conducted remotely using videoconferencing (HIPAA-compliant University of Minnesota Health Care Component Zoom). The study staff administering each questionnaire will display the questions and response options on the Zoom screen. In addition, study staff may read the questions aloud if the participant prefers. The participant will provide a verbal response for all measures. All procedures will be conducted for research purposes.

Table 3: Schedule of Measures

W1	W2	W3	W4	W5	W6	W7	W8
Χ							
Χ							Х
	Χ						X X X
Χ							X
Χ							Χ
Χ							Χ
Χ							X
Χ							Χ
Χ							
Χ							
							Χ
Χ							
Χ							
Χ							
Χ							
Χ							Χ
	X X X	X	X	X	X	X	X X X X X X X X X X X X X X X X X X X

NCT05029284

VERSION DATE: 07.21.2023

Unsupervised blood pressure (3	Χ		X
min/day for 7 days)			
activPAL 8-day monitoring (10	Χ		X
min instruction, 2 min/day)			
Interview 1 (30 min)		Χ	
Interview 2 (30 min)			X

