13.0 Risks to Participants

13.1 Foreseeable Risks:

- Distress or fatigue associated with clinical questionnaires, performance measures, interviews, or intervention performed as part of participation in the study: Questionnaires, performance measures, interviews, and intervention will be delivered by research assistants trained and supervised by the PI, an occupational therapist with more than 10 years of experience working with the stroke population. Participants who experience distress, embarrassment, or fatigue will be able to take breaks during testing and intervention session. If needed, testing may be completed in multiple short sessions.
- Discomfort or mild skin irritation associated with the activPAL activity monitoring protocol: The adhesive used to adhere the ActivPAL monitor to the participant's thigh is a common adhesive used in the healthcare setting. Participants who have a history of skin irritation are excluded from the study. Participants will receive instructions to monitor their skin for signs of irritation. If skin irritation occurs during the study, the participant will be instructed to transfer the activPAL to the opposite leg and continue to monitor for signs of irritation. Should irritation persist, participants will be instructed to remove the device and alternative strategies for activity monitoring will be explored (e.g., alternative wearing).

NCT05029284

VERSION DATE: 07.21.2023

schedules, use of non-adhesive strategies for maintaining device position).

- Risk for injury (such as a fall-related injury) while engaging in daily activities planned during intervention processes:

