18.0 Provisions to Monitor the Data to Ensure the Safety of Participants

- 18.1 Data Integrity Monitoring. Data integrity will be monitored by the PI, who has over 10 years of experience working with people with stroke-related disability in clinical (as an occupational therapist) and research settings. The following strategies will be applied:
 - 1. The study team will notify the PI of new study enrollments and the PI will review the screening documentation form within 2 business days to confirm eligibility to proceed with the informed consent meeting.

Page 34 of 44

VERSION DATE: 07.21.2023

- 2. Procedural checklists will be reviewed for completeness following each study visit by the study staff responsible for each visit. Reasons for missing data will be documented in REDCap.
- 3. The PI will hold weekly meetings with the study team to review study enrollment, monitor volunteer progression through study procedures, review case report forms, and monitor adverse events. Meetings will be documented and meeting minutes will be stored electronically with the study files in the University of Minnesota Box Secure Storage.
- 18.2 Data Safety Monitoring. This study will be overseen by a data safety monitor external to the trial and institution who has expertise in neurorehabilitation trials. The PI will meet with the data safety monitor every 6 months to review a report that includes: participant accrual, adverse events data, and data completeness. Adverse events data will be collected at two timepoints during the study: (1) during the interview 1 session, and (2) during post-intervention assessments. Data will be collected over the telephone or Zoom using a questionnaire. Ad hoc reports of adverse events will also be collected by any study staff who become aware of an adverse event during any study interaction. Whomever first identifies the adverse event will complete an ad hoc form and notify the PI who will determine appropriate follow-up actions and reporting.

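### The safety outcome in 3.2 stops at week 7, so a treatment-related event between then and the week 8 assessment may be known to the study yet not counted

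*Combined protocol and SAP*

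**What the plan says.** - **Outcome (3.2).** Safety is a secondary outcome: treatment-related serious and non-serious "adverse events that occur during the intervention period (weeks 2 through 7").
- **Schedule (5.1).** Participants "participate in 12 intervention sessions over 6 weeks (weeks 2 through 7"). The post-intervention assessment is in week 8.
- **Homework (4.1, Table 2).** One row covers sessions 3 to 12. Its content includes "Modify existing ICAN Plan, or Develop new ICAN Plan", and its homework is to carry out the plan. Session 12 is not excepted.
- **Homework (narrative).** Section 4.1 says "Participants are instructed to carry out the plan between sessions", and section 2.0 says "participants complete scheduled activities between sessions".
- **Where the risk lies (13.1).** The foreseeable injury risk is described as "Risk for injury (such as a fall-related injury) while engaging in daily activities planned during intervention processes".
- **Collection (18.2).** Scheduled collection takes place "1) during the interview 1 session, and (2) during post-intervention assessments". In addition, "Ad hoc reports of adverse events will also be collected by any study staff". The look-back period of the questionnaire is not stated.
- **Analysis (15.1, 15.3).** An adverse event count is compared with a benchmark of at most 1. Neither section repeats the week window or the treatment-related limit.

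**The concern.** The intervention sessions are mainly conversation. The physical risk lies in the activities that participants plan in a session and carry out afterwards. A window that closes with the last week of sessions may therefore close before the last planned activity has been done. Under Table 2 as written, a plan made at session 12 could be carried out in week 8. A fall during that activity could be reported at the week 8 assessment or to any staff member, be judged treatment-related, and still not belong to the safety outcome.

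What is at stake is the reported safety result. Safe remote delivery is part of Aim 1, and the findings feed a later randomized trial. With a benchmark of at most 1 event, a single event can decide how the comparison reads.

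**Working it through.** The plan states no figure for this point, so there is none to reproduce. The check is a comparison of the sections, followed by bounds on the exposure.

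**Timeline**

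1. Table 2 numbers intervention weeks 1 to 6. Section 5.1 places them in study weeks 2 to 7, so session 12 falls in study week 7.
2. The 3.2 window closes at the end of week 7.
3. The post-intervention assessment falls on some day in week 8. The gap between the two is therefore from almost nothing to about one week.
4. Under 18.2, an event in that gap can reach the study by questionnaire or ad hoc. No section assigns it to the 3.2 outcome.
5. Whether anyone is exposed in the gap depends on session 12. Table 2 implies a plan follows it. The two narrative statements about activity between sessions imply none does. Even if one does, it may be completed within week 7.

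**Exposure bounds**

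Let d be the weeks of plan activity after week 7 and before the assessment. The share of time at risk that goes uncounted is q = d / (6 + d).

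| d (weeks) | q |
|---|---|
| 0 | 0% |
| 0.5 | 0.5/6.5 = 1/13 = 7.7% |
| 1 | 1/7 = 14.3% |

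For the 5 to 10 completers in 10.1, the counted time is 5 × 6 = 30 to 10 × 6 = 60 participant-weeks. At d = 1 the uncounted time is 5 to 10 participant-weeks.

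**Effect on the benchmark: illustrations only**

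Both illustrations assume an even weekly risk, a benchmark read as a study total, and a 15.3 count that uses the 3.2 window. The documents state none of these.

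- *Given exactly two treatment-related events by the assessment*, the chance that at least one is uncounted is 1 − (1 − q)². This is 0% at d = 0, 1 − (12/13)² = 25/169 = 14.8% at d = 0.5, and 1 − (6/7)² = 13/49 = 26.5% at d = 1.
- *Without conditioning on two events*, use a Poisson count with mean m = n × rate × weeks, so that P(at most 1) = e^(−m)(1 + m). The rates are assumed at 0.005 to 0.05 events per participant-week, with a full extra week (d = 1):

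| n | Rate | Weeks 2–7 | Weeks 2–8 | Difference |
|---|---|---|---|---|
| 5 | 0.005 | 0.990 | 0.986 | 0.003 |
| 5 | 0.01 | 0.963 | 0.951 | 0.012 |
| 5 | 0.02 | 0.878 | 0.844 | 0.034 |
| 5 | 0.05 | 0.558 | 0.478 | 0.080 |
| 10 | 0.005 | 0.963 | 0.951 | 0.012 |
| 10 | 0.01 | 0.878 | 0.844 | 0.034 |
| 10 | 0.02 | 0.663 | 0.592 | 0.071 |
| 10 | 0.05 | 0.199 | 0.136 | 0.063 |

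On these assumptions the longer window changes the reading in about 0.3% to 8% of studies. At d = 0 the change is zero.

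**The case against.** The strongest reply is that 3.2 uses an ordinary on-treatment window, which matches the schedule in 5.1. The week 8 questionnaire is needed anyway, to cover the time from interview 1 to the end of week 7. Collecting more than the outcome counts is common practice. This stands: a reader might infer that 3.2 and 18.2 contradict each other, and they do not.

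The reply continues that exposure after session 12 is unproven. The narrative places activity between sessions, and no session follows session 12 at which a plan could be reviewed. The Table 2 row may simply be a generalisation. This also stands, and it is why the lower bound is nil. It does not settle the matter, because the table makes no exception for session 12.

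A reader might also infer that a week 8 event is sure to be collected and then dropped from the benchmark. The documents do not support either half. Section 18.2 gives no look-back period. Section 15.3 repeats neither the window nor the relatedness limit, so read literally its count could already include the event. In that case the outcome and its benchmark would count different events, which is another reason to state one definition.

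Finally, the 14.8% and 26.5% figures might be taken as the chance that the benchmark is misread. They hold only if exactly two events have occurred. With none or one, the window cannot change the reading against a study-total benchmark.

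**Conclusion.** The point holds as a minor one, in conditional form. The 3.2 rule can exclude a treatment-related event that the study knows about, provided that a plan is carried out after week 7 and the event precedes the week 8 assessment. It affects the benchmark only if 15.3 takes its window from 3.2.

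The uncounted exposure lies between nil and about one week per participant. The effect on the result cannot be determined, because the documents give no event rate and do not say whether the benchmark is a study total or applies per participant.

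A reader might infer a gap in participant protection. There is none here: adverse events that come to light go to the principal investigator, and adverse event data go to the external safety monitor whatever the outcome window. Nor does a formal decision turn on the count. The comparison is descriptive, in a formative case series, and no go/no-go rule is attached to it.

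**What to change.** - **3.2:** run the safety window from intervention session 1 through the post-intervention (week 8) assessment, and keep the treatment-related limit.
- **15.3:** state that the adverse event count uses the 3.2 definition.
- **18.2:** as a supporting detail, have the post-intervention questionnaire ask about events up to the day it is given, since no look-back period is stated.
- **Attendance:** leave at weeks 2 through 7.

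The cost is about one line in each of the three sections. No new visit, form or staff is needed, because adverse events are already collected at that assessment. The downside is that the count may be slightly less favourable. The new end point also remains partly a convention, since a participant could continue a plan after the assessment.
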